## 2.4.2 Primary Efficacy Variable

### **Main statistical model and adjustment for covariates**

The primary analysis will be performed using the mITT with a Negative Binomial regression model to accommodate the potential over-dispersed data appropriately. The model will include the total number of confirmed relapses with onset between randomization date and the day of last treatment as response variable, treatment group, EDSS strata (baseline EDSS score  $\leq 3.5$  versus  $> 3.5$ ) and clinic region (defined in section 2.1.1) as covariates. There will be two treatment groups (teriflunomide or ublituximab). In order to account for different treatment durations among subjects, the log-transformed standardized treatment duration will be included in the model as an “offset” variable for appropriate computation of the annualized relapse rate. [REDACTED] will be used to assess the overall model with subjects in a repeated statement using a Generalized estimating equation (GEE) approach. The standardized treatment duration is defined as (date of last treatment – randomization date +1)/365.25.

Two-sided 95% confidence intervals of the rate ratio will be provided for the comparisons of ublituximab versus teriflunomide. The estimated relapse rate for each treatment group and the difference between them, together with the corresponding 2-sided 95% confidence intervals will be provided.

[REDACTED]

The “overall” estimated annualized relapse rates (number of relapses divided by the sum of years under treatment) will also be presented by treatment group.

### **Other analysis population for the primary efficacy variable**

Analysis of annualized relapse rate will also be performed using the ITT and PP populations as a supportive analyses.

### **Handling of dropouts**

Dropouts are handled by using the offset variable in the model which adjusts for the duration of time on treatment. This is different than multiple imputation, which seeks to estimate the information that would be available after dropping out. The primary analysis includes confirmed relapses with onset from randomization to date of last treatment. Subjects who withdraw from study drug treatment can still be followed and participate in study visits. However, the primary analysis will only include the time from randomization until the date of last treatment.

### **Subgroup analysis**

Subgroup analyses will be performed for the primary efficacy variable by:

- Gender
- Race
- Age category (<38, ≥38)
  - Age of 38 is expected to be close to the median age of all randomized subjects
- Regions as defined in 2.1.1
- Baseline EDSS strata (<3.5, ≥3.5)
- Number of relapses experienced in the 2 years prior to study start (≤1, 2, 3, and ≥4)
- Received approved disease modifying MS drug prior to enrollment (Yes, No)
- Number of baseline Gd-enhancing lesions (0, ≥1)

The GEE method will be used to assess consistency of treatment effects across the subgroup levels, utilizing a treatment-by-subgroup interactions test at significance level of 0.05, and forest plots of the group comparisons of ARR and their confidence intervals. Each subgroup factor will be assessed separately. The model will include treatment, EDSS strata, region, subgroup, and treatment-by-subgroup interaction as fixed effects, log-transformed standardized treatment duration as an offset variable. In addition, summary statistics of relapse rates will be provided for each subgroup, based on the model for each subgroup, including treatment, EDSS strata and region as covariates.

### Sensitivity Analysis

1. The primary analysis will be repeated based on all reported MS relapses (rather than just confirmed ones).
2. A time to relapses analysis using Cox proportional hazards model with first IRAP-confirmed relapse as the primary event will be conducted to compare with the primary analysis in a negative binomial model. The Cox proportional hazards model will be specified with treatment, region, number of relapses in previous year, baseline EDSS score strata (<3.5, ≥3.5), baseline number of T1 Gd-enhancing lesions, sex, and the subject's age at baseline as covariates.
3. To assess the effects of treatment withdrawals, the primary analysis will be repeated using the information on relapses which occur during the period following drug withdrawal to the end of the study period regardless of whether additional treatment were utilized. Relapses which occurred after permanent discontinuation of study medication will be included and natural log (time on study in years) rather than the natural log (time on study drug in years) will be used as the offset variable in the negative binomial model, which is the primary analysis.
4. We will examine the dropouts from the trial using all participants who provided withdrawal of consent excluding deaths. Multiple imputation will be used to impute the expected number of relapses a participant would have had if they had continued to participate in the trial. To perform the imputation, 10 replicates will be used since a relapse on treatment is relatively low frequency event. The covariates used to model and predict the imputations will include: treatment, region, number of relapses in previous year, baseline EDSS score strata (<3.5, ≥3.5), baseline number of T1 Gd-enhancing lesions, sex and the subject's age at baseline as covariates.

5. For secondary outcomes T1 Gd enhancing, T2 NELs, and 12 week CDP, the effects of dropouts and study discontinuations will be similarly evaluated as number 4 above.
6. Additional sensitivity analyses may be conducted as needed

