4.4.3 RE-CONSENT CRITERIA AFTER RELAPSING

If a relapse is confirmed by IRAP and/or deemed a Treating Neurologist medically confirmed relapse, the following actions will be taken:

- The subject will be reminded of the current approved MS medications/treatments and the opportunity to terminate the study and be treated with an approved MS medication.
- The subject will be requested to re-sign an informed consent form within 6 weeks after first reporting of the suspected relapse if he/she chooses to continue to participate in the study, in the same treatment assignment.

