8.9.3 SENSITIVITY ANALYSES

Sensitivity Analysis

1. The primary analysis will be repeated based on all reported MS relapses (rather than just confirmed ones).
2. A time to relapses analysis using Cox proportional hazards model with first IRAP-confirmed relapse as the primary event will be conducted to compare with the primary analysis in a negative binomial model. The Cox proportional hazards model will be specified with treatment, region, number of relapses in previous year, baseline EDSS score, baseline number of T1 Gd-enhancing lesions sex and the subject's age at baseline as covariates.
3. To assess the effects of treatment withdrawals, the primary analysis will be repeated using the information on relapses which occur during the period following drug withdrawal to the end of the study period regardless of whether additional treatment were utilized. Relapses which occurred after permanent discontinuation of study medication will be included and natural log (time on study in years) rather than the natural log (time on study drug in years) will be used as the offset variable in the negative binomial model, which is the primary analysis.
4. We will examine the dropouts from the trial using all participants who provided withdrawal of consent excluding deaths. Multiple imputation will be used to impute the expected number of relapses a participant would have had if they had continued to participate in the trial. To perform the imputation, 10 replicates will be used since a relapse on treatment is relatively low frequency event. The covariates used to model and predict the imputations will include: treatment, region, number of relapses in previous year, baseline EDSS score, baseline number of T1 Gd-enhancing lesions sex and the subject's age at baseline as covariates.
5. For secondary outcomes T1 Gd enhancing, T2 NELs, and 12 week CDP, the effects of dropouts and study discontinuations will be similarly evaluated as number 4 above.
6. Additional sensitivity analyses may be defined in the analysis plan prior to database lock.

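### The imputation for consent withdrawals lists only treatment and baseline predictors, so Sensitivity Analysis 4 carries an error of its own; condition it on each subject's on-study relapses and exposure

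*SAP*

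**What the plan says.** SAP 2.4.2, Sensitivity Analysis, item 4 deals with one group: "We will examine the dropouts from the trial using all participants who provided withdrawal of consent excluding deaths". For them, "Multiple imputation will be used to impute the expected number of relapses a participant would have had if they had continued" in the trial. The predictors are given as follows: "The covariates used to model and predict the imputations will include: treatment, region, number of relapses in previous year", then baseline EDSS stratum, baseline Gd-enhancing lesion count, sex and age. Protocol 8.9.3 item 4 has the same list with EDSS as a score: "The covariates used to model and predict the imputations will include: treatment, region, number of relapses in previous year, baseline EDSS score", and so on. The number of replicates is fixed ("To perform the imputation, 10 replicates will be used since a relapse on treatment is relatively low frequency event"), but the imputation distribution is not named. Apart from treatment, every listed predictor is a baseline variable.

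For Gd-enhancing lesions, new or enlarging T2 lesions and 12-week CDP, item 5 says only that "the effects of dropouts and study discontinuations will be similarly evaluated as number 4 above".

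Three other provisions matter here:

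- Protocol 4.4.3: after each confirmed relapse the subject is reminded of approved alternatives and of "the opportunity to terminate the study and be treated with an approved MS medication", and must re-sign consent within 6 weeks of first reporting the relapse in order to stay.
- Protocol 3.3: data collection stops on the day consent is withdrawn, unless the subject signs a separate consent for the 20-week follow-up.
- SAP 2.1.3.1 and Protocol 4.4.1: relapses after study drug is stopped are used in sensitivity analysis only while consent stands. Item 3 therefore does not cover the subjects whom item 4 addresses.

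**The concern.** The protocol creates a direct route from relapse to withdrawal. The plan also chooses a negative binomial model because it expects over-dispersion, that is, subjects who differ in underlying relapse rate. Under that model, a subject who has already relapsed is expected to relapse more often afterwards than others with the same baseline profile. An imputation that uses only treatment and baseline covariates gives such a subject the average rate for that profile.

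Item 4 is the one specified analysis aimed at consent withdrawals. If it omits a variable that may both drive withdrawal and predict the outcome, a difference between it and the primary analysis could come from the imputation alone, and agreement could not be taken as confirmation.

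**Working it through.** **1. Inputs.** From the documents (SAP 1.3.1 and its Table 1): annualized relapse rates 0.25 and 0.15 at a pooled rate of 0.20; 40% reduction; average follow-up 1.75 years; 10% dropout allowance. Two-sided 0.05 (SAP 2.4). Treatment period 672 days, or 672/365.25 = 1.84 years. Not available in the public text: power and the dispersion k. Not in the documents at all: the probability of leaving after a relapse.

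**2. Reproducing the plan's table to obtain k.** With t = 1.75, rates m1 and m2, and pooled rate m:

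N = [z(0.975)·√V0 + z(power)·√V1]² / (ln 0.6)², where V1 = 1/(t·m1) + 1/(t·m2) + 2k and V0 = 2/(t·m) + 2k.

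At m = 0.20, k = 0.805 and 80% power: V0 = 2/0.35 + 1.61 = 7.324 and V1 = 1/0.4375 + 1/0.2625 + 1.61 = 7.705. N = (1.960 × 2.706 + 0.842 × 2.776)² / 0.2609 = 223.7. Table 1 gives 224 (the text gives 219).

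Across all nine columns the formula gives 267.5, 243.2, 223.7, 207.8, 194.5, 183.3, 173.6, 169.3 and 165.3. The table has 268, 243, 224, 208, 195, 183, 174, 169 and 165, so the largest error is 0.25%. At 0.19 the formula gives 232.9 (text: 233). The best fits at 85% and 90% power miss by up to 3.3% and 10.1%. So k is about 0.8; this is an inference from the table, not a stated value.

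**3. What one relapse implies.** In a gamma-Poisson model the expected future rate after y relapses in t years is m·(1/k + y)/(1/k + m·t). With k = 0.805 (1/k = 1.242), y = 1 and t = 1:

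- Teriflunomide: 0.25 × 2.242/1.492 = 0.376 per year, 1.50 times the arm average.
- Ublituximab: 0.15 × 2.242/1.392 = 0.242 per year, 1.61 times the arm average.

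For k from 0.3 to 1.5 the multiple at 1 year runs from 1.21 to 2.04.

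**4. Effect on the rate ratio.** Gamma-Poisson simulation with k = 0.8, 1,000,000 subjects per arm, 672 days, and withdrawal only after a relapse. Leaving probabilities are teriflunomide/ublituximab.

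| Leaving after a relapse | Dropout | Full data | Negative binomial with offset | Imputed, arm and baseline only | Imputed, also given own count and exposure |
|---|---|---|---|---|---|
| 30% / 30% | 12.3% / 7.7% | 0.602 | 0.602 | 0.612 | 0.601 |
| 40% / 10% | 15.7% / 2.7% | 0.602 | 0.602 | 0.634 | 0.603 |
| 10% / 50% | 4.4% / 12.3% | 0.602 | 0.603 | 0.585 | 0.603 |

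In the first row the true post-withdrawal rates are 0.435 and 0.264, while the imputation uses 0.250 and 0.151. The imputed arm rates are 0.2385 and 0.1460, against 0.2503 and 0.1505 with full data.

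Consistency check: the shortfall should equal dropout × share of follow-up lost × rate gap. Teriflunomide: 0.0118 = 0.123 × f × 0.185 gives f = 0.52. Ublituximab: 0.0045 = 0.077 × f × 0.113 gives f = 0.52. Losing about half of follow-up is plausible, and the arms agree.

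**5. Range.** With k = 0.3, 0.7 and 1.5 and leaving at 30/30%, 50/50% and 50/10%, the baseline-only rate ratio runs from 0.607 to 0.667. The conditional version stays within 0.003 of full data throughout. The largest shift, about 0.07, needs both k = 1.5 and 50/10% leaving.

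**6. Limits.** Baseline covariates other than arm were not simulated; where they explain part of the between-subject variation, the shift is smaller. Item 5 was not calculated.

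**The case against.** The strongest reply is that the list says the predictors will include these variables, not that they are the only ones. Since no model is named, a negative binomial draw could condition on the observed count without listing it as a covariate. That is fair: the documents do not forbid it. They do not state it either, and the list is the only specification of the imputation, so the key choice is left to programming.

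Second, the shift is small, rests on leaving probabilities that are not in the documents, and in the equal-leaving case moves toward no effect. This stands. That case loses an average of (12.3 + 7.7)/2 = 10.0% of subjects, matching the plan's whole dropout allowance, but it attributes all of that loss to relapse.

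Third, relapses observed before withdrawal still count, item 3 covers subjects who stop drug but keep consent, and item 6 allows further analyses. All true. The error is confined to time after withdrawal, but that time is all that item 4 adds, and an unspecified further analysis does not repair a specified one.

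Fourth, for item 5 the predictors are inferred from the reference back to item 4. This also stands; there the point is a request to specify.

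**Conclusion.** As listed, the item 4 imputation understates relapse rates after a relapse-driven withdrawal. Sensitivity Analysis 4 then departs from the planned negative binomial analysis through an artefact of the imputation: about 0.01 on the rate ratio with equal 30% leaving, +0.03 with 40%/10% and −0.02 with 10%/50%. These figures rest on a gamma-Poisson model, k of about 0.8 inferred from Table 1, and assumed leaving probabilities.

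Three stronger readings are tempting and not supported:

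- A reader might infer that item 4 would simply reproduce the unimputed result and so reassure falsely. That is true only of the crude rate (relapses over treatment years), which SAP 2.4.2 also reports: in a second simulation with 400,000 per arm and 30% leaving within 6 weeks, the crude teriflunomide rate was 0.2375 and the baseline-only imputed rate 0.238, against 0.249 with full data. The planned model, with its offset, already uses each subject's count and exposure, and item 4 differs from it.
- A reader might infer that relapse-driven dropout biases the primary test. In these scenarios the primary estimate is within about 0.001 of full data.
- A reader might infer that missing at random fails. Withdrawal that depends on observed relapses is still missing at random; it is the imputation model that lacks a predictor.

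The conclusion is limited to a supportive analysis whose agreement or disagreement with the primary result is hard to interpret as specified.

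**What to change.** In item 4 of SAP 2.4.2, and in Protocol 8.9.3 if it is amended, name the imputation model and draw post-withdrawal relapses from a negative binomial conditional on the subject's observed on-study relapse count y and exposure t. For remaining time r, the mean is r·m·(1/k + y)/(1/k + m·t), with m predicted from the covariates already listed, which should all be kept.

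In item 5, state that the imputation for Gd-enhancing and T2 lesions also uses the subject's earlier post-baseline counts, and that for CDP it uses the last EDSS change from baseline and an indicator of progression not yet confirmed at withdrawal.

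All of these variables are already collected. The cost is SAP wording and minor programming before database lock, with no new data.

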## 2.4.3 Secondary Endpoints

### 2.4.3.1 Statistical testing Strategy

Once the null hypothesis of the primary analysis has been rejected, the key secondary outcomes will be tested using a hierarchical approach with the order specified below using a step-down procedure where each test is at a Type I error 0.05. If any endpoint fails to reach significance, then formal testing of significance of the subsequent secondary outcomes will not be performed. All p-values will be reported and will be interpreted as either confirmatory or non-confirmatory (i.e., descriptive only).

[figure not shown]
1. Total number of gadolinium enhancing (Gd-enhancing) T1-lesions per MRI scan by Week 96.
2. Total number of new and enlarging T2 hyperintense lesions (NELs) per MRI scan by Week 96
3. Time to confirmed disability progression (CDP) for at least 12 weeks occurring during the 96-week, double-blind, treatment period (pooled analysis with Study TG1101-RMS302). \*
4. Proportion of subjects with no evidence of disease activity (NEDA) from Week 24 to Week 96.
5. Proportion of subjects reaching impaired SDMT (Symbol Digit Modalities Test) from baseline to Week 96.
6. Percentage change in Brain Volume from baseline to Week 96.

\* Confirmed Disability Progression for at least 12 weeks during the 96-week treatment period will be analyzed using pooled data from the two identical studies TG1101-RMS301 and TG1101-RMS302.

For all tests other than #3 (12-week CDP), the testing will be based on Study ULTIMATE II individually, at  $\alpha=0.05$ .

For #3, 12-week CDP endpoint, the testing will be based on pooled data from both Studies ULTIMATE I and ULTIMATE II achieve sufficient statistical power to detect relevant treatment differences. Therefore, this test will not be performed until data from both studies are available. Specifically, this test is considered confirmatory only if all tests for the primary endpoint and all secondary endpoints before this test (i.e. #1 & #2) are statistically significant at  $\alpha=0.05$  level in both studies. Once this test is statistically significant, all subsequent tests (#4-6) will continue at  $\alpha=0.05$  level within each individual study.

The statistical testing sequence is illustrated below.

### 2.4.3.2 MRI

The following MRI results will be provided by the central lab:

Measurement/Visit	SCREENING	WEEK 12 DAY 84	WEEK 24 DAY 168	WEEK 48 DAY 336	WEEK 96 DAY 672	EARLY WITHDRAWAL FROM TREATMENT
T1 Unenhancing Lesion Count	X					
T2 Lesion Count	X					
New Enlarging T2 Lesion Count			X (Screening)	X (Previous)	X (Previous)	X (Previous)
New Enlarging T2 Lesion Volume			X (Screening)	X (Previous)	X (Previous)	X (Previous)
T2 Lesion Volume	X		X	X	X	X
New T1 Unenhancing Lesion Count			X (Screening)	X (Previous)	X (Previous)	X (Previous)
T1 Unenhancing Lesion Volume	X		X	X	X	X
Normalized Brain Volume	X					
Brain Volume			X	X	X	X
Gad Enhancing Lesion Count	X	X	X	X	X	X

Gad Enhancing Lesion Volume	X		X	X	X	X
-----------------------------	---	--	---	---	---	---

The analysis endpoints will be derived as follows:

Protocol endpoint	MRI test result to be used	Derivation
total number of gadolinium enhancing (Gd-enhancing) T1-lesions per MRI scan by Week 96	Gad Enhancing Lesion Count (GADCNT)	$[GADCNT(w12)+GADCNT(w24)+GADCNT(w48)+GADCNT(w96)]/[number\ of\ MRIs\ available\ (w12/w24/w48/w96)]$ Note: the division by the number of MRIs will be accomplished by an offset in the negative binomial regression
Total number of new and enlarging T2 hyperintense lesions (NELs) per MRI scan by Week 96	New Enlarging T2 Lesion Count (NEWT2CNT)	$[NEWT2CNT(w24)+\ NEWT2CNT(w48)+\ NEWT2CNT(w96)]/[number\ of\ MRIs\ available\ (w24/w48/w96)]$ Note: the division by the number of MRIs will be accomplished by an offset in the negative binomial regression
Volume of hypointense T1 lesion component (black holes)	T1 Unenhancing Lesion Volume (T1UNVOL)	T1UNVOL (w24) , T1UNVOL (w48) ,T1UNVOL (w96)
Volume of T2 lesion	T2 Lesion Volume (T2VOL)	T2VOL(w24), T2VOL(w48),T2VOL(w96)
MRI part of NEDA definition (no T1 Gd+ lesions and no new/enlarging T2 lesions)	Gad Enhancing Lesion Count (GADCNT), New Enlarging T2 Lesion Count (NEWT2CNT)	All values , GADCNT(w24), GADCNT(w48), GADCNT(w96), NEWT2CNT(w24), NEWT2CNT(w48), NEWT2CNT(w96) need to be zero
Percent change in brain volume as detected by MRI compare to baseline	Brain Volume (BV)	$(BV(w24) - NBV(baseline))/NBV(baseline)*100$ $(BV(w48) - NBV(baseline))/NBV(baseline)*100$ $(BV(w96) - NBV(baseline))/NBV(baseline)*100$
Total volume of Gd-enhancing T1 lesions per MRI scan over the treatment period	Gad Enhancing Lesion Volume (GADVOL)	$[Sum\ of\ all\ post-baseline\ GADVOL(w24/w48/w96)]/[number\ of\ MRIs\ available\ (w24/w48/w96)]$

MRI data will only be used for analysis if not rejected or invalid, e.g. due to change of scanner, indicated as comments from the central lab.

MRIs will also be excluded from analysis if corticosteroids (ATC level 2 = “CORTICOSTEROIDS FOR SYSTEMIC USE”) were dosed within 30 days prior to the scan.

The MRI count variables (Total Number of gadolinium enhancing (Gd-enhancing) T1-lesions per MRI scan at Weeks 12 (where applicable), 24, 48, and 96, Total number of new and enlarging T2 hyperintense lesions (NELs) per MRI scan at Weeks 24, 48, and 96) will be assessed for differences between the treatment groups using negative binomial regression with an offset based on the log-transformed number of post-baseline MRI scans and covariates region, baseline EDSS strata, and corresponding baseline lesion count.

For analysis of percent brain volume change from baseline, a Mixed Model Repeated Measures (MMRM) analysis will be implemented via [REDACTED] by fitting percent change from baseline values on the cube root transformed volume from all visits after baseline in the treatment period with scheduled assessments of brain volume. The models will include factors (fixed effects) for treatment, region, baseline EDSS strata, visit, treatment-by-visit interaction, and baseline value of

the brain volume (cubic root transformed). The factor, visit, with nominal visits to avoid undue reliance on a linear in time effect will have 3 levels (Week 24, Week 48 and Week 96). An unstructured correlation matrix will be used to model the within-patient errors. Parameters will be estimated using restricted maximum likelihood method with the Newton-Raphson algorithm. Denominator degrees of freedom will be estimated using Satterthwaite's approximation.

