⁴ Weeks 8 and beyond, collections/assessments may occur ± 5 days from specified time points, except for MRI scans, which can occur ± 7 days on Weeks 12 and 96 and must be performed pre-infusion on infusion days (- 7 days) on Weeks 24 and 48. MRI scan at Early Withdrawal from Treatment Visit should be performed within 4 weeks after withdrawing from the study.

⁵ Prior to each infusion except PT/INR which is completed at baseline. Urine Pregnancy Test on non-infusion days subjects will test upon arrival at the site

⁶ Prior to infusion and 30 minutes +/- 15 minutes post-infusion on infusion days. For non-infusion days, one PK sample should be obtained

⁷ Anti-Drug Antibodies are antibodies developed against ublituximab

⁸ Physical examination will occur on all visits except Week 1 Day 2 and Week 2 Day 8

⁹ Within 2 hours pre-infusion and 60 minutes +/- 15 minutes post-infusion on any infusion day

¹⁰ Re-consent following a suspected relapse is required if the relapse is confirmed by IRAP or by the Treating Neurologist (Treating Neurologist medically confirmed relapse), whichever comes first. Re-consent must occur within 6 weeks after first reporting of relapse. Re-consent may occur at the next schedule office visit but may require an unscheduled visit if the relapse occurs between Weeks 24 and 96 (where the frequency of scheduled visits is every 12 weeks).

¹¹ Serum pregnancy test must be completed within 5 days prior to Week 1 Day 1

¹² Obtain blood sample for teriflunomide drug concentration test prior to first dose of accelerated teriflunomide elimination procedure

¹³ Prior to each infusion

¹⁴ The Unscheduled Relapse Visit will be conducted if a possible relapse is reported by the subject. The visit is to be planned as soon as possible, within 7 days from subject notification of the relapse to the site. Infusion visit is delayed until relapse is back to baseline, or Treating Neurologist/PI does not expect any improvements.

¹⁶ Teriflunomide/oral placebo administration shall be taken in the morning until the last day of Week 95. Alternative dosing times are allowed if necessary.

¹⁷ Sample for teriflunomide concentration to be collected before the first oral dose of teriflunomide/oral placebo

¹⁸ For Unscheduled Relapse Visit, EDSS assessment (by Examining Neurologist) and neurological examination (by Treating Neurologist) will be performed independently

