6.3.3 RADIOLOGICAL EVALUATION

Magnetic Resonance Imaging (MRI) is a useful tool for monitoring CNS lesions in MS. Different MRI derived parameters have been related to clinical activity and T1 weighted gadolinium-enhancing lesions or new and/or enlarging hyperintense T2 lesions have been related to relapses. It is hypothesized that changes in brain volume may reflect brain atrophy as a result of MS-related tissue loss and may thereby correlate with long-term clinical outcomes in RMS subjects.

Brain MRI scans will be obtained in all subjects as detailed in the Schedule of Assessments in Section 6. In addition, brain MRI scans will be obtained in subjects who had withdrawn from the trial. Scans will be performed by trained and certified MRI technicians.

Assessment of effect on Gd enhancing lesion and new, enlarging T2 lesions, brain volume, T1 hypointense will be evaluated as outlined in the schedule of events by a central reader. The following time windows apply:

- “Baseline” MRI should be performed after informed consent is obtained, but preferably 10 days prior to the Week 1 Day 1 visit.
- MRI are scheduled as follows: Weeks 12 (+/- 7 days), 24 (pre-dose; - 7 days), 48 (pre-dose; - 7 days) and 96 (+/- 7 days)
- MRI scans may be performed on the day of withdrawal or within 4 weeks after withdrawing from the study.
 - The MRI may not be needed if an MRI was obtained within 30 days prior to withdrawal from the trial.

If subjects receive corticosteroids for a relapse, every effort should be made to obtain the scan prior to the first steroid dose if the pre-steroid scan is within 1 week of the scheduled visit. In subjects receiving corticosteroids, there should be an interval of at least 30 days between the last dose of corticosteroids and the scan.

At each time point, the MRI will include acquisition of scans with and without intravenously administered gadolinium contrast enhancement.

MRI scans will be read by a centralized reading center located in Montreal, Canada for efficacy endpoints. The centralized reading center is blinded to the treatment assignment and the reading is performed in the absence of clinical information. Additional details on scanning acquisition sequences, methods, handling and transmission of the scans, certification of site MRI radiologists/technicians, and the procedure for the blinded analysis of the scans at the central reading center will be described in a separate MRI Manual.

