## 2.2.3 Modified Intention-to-Treat (mITT) Population

The modified Intention-to-Treat (mITT) population will consist of all subjects in the ITT population who received at least one dose of study medication and have at least one baseline and post baseline efficacy assessment. The primary efficacy analyses (of primary, secondary and tertiary efficacy endpoints, except MRI related) will be performed based on the mITT population.

The MRI related efficacy analyses will be performed on the subjects in mITT population who have baseline and post-baseline MRI efficacy assessments (mITT-MRI).

Subjects will be analyzed by randomized treatment group.

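### Key secondary lesion counts leave out the centrally read Early Withdrawal MRI, and some subjects in the MRI analysis set have no contributing scan, so their offset is log(0)

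*SAP*

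**What the plan says.** The scan is planned. Protocol 6.3.3 states that "brain MRI scans will be obtained in subjects who had withdrawn from the trial", and a footnote to the schedule tables in Protocol 6 adds that "MRI scan at Early Withdrawal from Treatment Visit should be performed within 4 weeks after withdrawing from the study". There is one exception: "The MRI may not be needed if an MRI was obtained within 30 days prior to withdrawal from the trial".

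The scan is read. The central-reading table in SAP 2.4.3.2 has a column headed "EARLY WITHDRAWAL FROM TREATMENT", marked for the Gd count and for the new or enlarging T2 count, the latter read against the previous scan. No T2 count is read at Week 12.

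The scan is not used in the counts. In the derivation table of the same section, Gd lesions are summed and divided over Weeks 12, 24, 48 and 96, and T2 lesions over Weeks 24, 48 and 96. For both, "the division by the number of MRIs will be accomplished by an offset in the negative binomial regression".

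The denominator is described in other ways elsewhere. The model text in SAP 2.4.3.2 takes the log of the post-baseline scan count, without limiting it to particular weeks. Protocol 8.9.2 divides by the total number of brain scans and then gives the model an offset based on time on study.

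On who is analysed, SAP 2.2.3 says: "The MRI related efficacy analyses will be performed on the subjects in mITT population who have baseline and post-baseline MRI efficacy assessments". On visit assignment, SAP 2.5.2 ties each MRI to its own visit and provides no reassignment.

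**The concern.** The analysis set and the denominator are not defined on the same scans. Membership needs any post-baseline MRI, while the denominator counts only named weeks. A subject can satisfy the first and score zero on the second, and the model then has no finite offset for that subject. The plan does not say what happens next. In practice the record is deleted, so subjects are excluded according to how early they withdrew, although a centrally read lesion count may exist for them.

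The two endpoints sit high in the testing order. Under SAP 2.4.3.1 they are tested first and second after the primary endpoint, and each gates everything below. The pooled 12-week disability progression test is confirmatory only if both succeed in both studies. Post-randomisation exclusions in such analyses should be few and governed by a written rule.

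**Working it through.** The plan states no figure on this point, so there is none to reproduce. The check has two parts.

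**Offsets by time of withdrawal.** Scheduled post-baseline MRIs are at Weeks 12, 24, 48 and 96. Assume that each scheduled scan up to withdrawal is valid and that a withdrawal scan is done. The offset is the log of the scan count. Each cell gives scans, then offset.

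| Leaves at | Gd, named weeks | T2, named weeks | All post-baseline scans | Gd, contributing scans incl. withdrawal | T2, contributing scans incl. withdrawal |
|---|---|---|---|---|---|
| Week 8 | 0, log(0) | 0, log(0) | 1, 0 | 1, 0 | 1, 0 |
| Week 18 | 1, 0 | 0, log(0) | 2, 0.693 | 2, 0.693 | 1, 0 |
| Week 30 | 2, 0.693 | 1, 0 | 3, 1.099 | 3, 1.099 | 2, 0.693 |
| Week 60 | 3, 1.099 | 2, 0.693 | 4, 1.386 | 4, 1.386 | 3, 1.099 |

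- *Named weeks (derivation table).* Leaving before Week 12 gives log(0) for both endpoints. Leaving between Weeks 12 and 24 gives log(0) for T2. The second case is the clearer one, because the Week 12 scan is a scheduled post-baseline MRI and so meets the set definition in SAP 2.2.3. In a test fit on 440 simulated records, 5 of them with log(0), the negative binomial model could not be estimated until those 5 were removed, leaving 435.
- *All post-baseline scans (model text).* The offset is finite, but the sum has no term for the withdrawal scan or, for T2, the Week 12 scan. The Week 30 leaver has T2 lesions from 1 scan set against 3, and Gd lesions from 2 set against 3. A completer has T2 lesions from 3 scans set against 4. That factor of 3/4 is the same for completers in both arms, but the mismatch is larger for early leavers.
- *Time on study (Protocol 8.9.2).* The offset is finite, but the Week 18 leaver has exposure and no T2 read in the sum.
- *Contributing scans, withdrawal included.* Every row is finite, and each counted scan has its lesions in the sum.

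**How many subjects.** Inputs: 220 per arm (SAP 1.3); a 10% dropout allowance (SAP 1.3.1, where 219 × 1.10 = 240.9, the plan's 241). The timing of dropout is not given and is assumed. The formula is 220 × dropout × fraction leaving before the week in question. *Even* timing puts 12/96 before Week 12 and 24/96 before Week 24. *Early* timing puts a quarter before Week 12 and a half before Week 24.

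| Dropout | Timing | Before Week 12 (no Gd scan) | Before Week 24 (no T2 scan) |
|---|---|---|---|
| 5% | even | 11 × 0.125 = 1.4 | 11 × 0.25 = 2.8 |
| 10% | even | 22 × 0.125 = 2.8 | 22 × 0.25 = 5.5 |
| 10% | early | 22 × 0.25 = 5.5 | 22 × 0.5 = 11 |
| 20% | early | 44 × 0.25 = 11 | 44 × 0.5 = 22 |

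The range is about 1 to 11 per arm for Gd and 3 to 22 per arm for T2. The T2 figure combines two groups, which are equal in size under both timings: those leaving before Week 12, and those leaving between Weeks 12 and 24 who already have a Week 12 scan.

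**The case against.** The strongest reply is that the omission is deliberate. Protocol 8.9.2 and both the derivation table and the model text of SAP 2.4.3.2 list the same weeks, and SAP 2.5.3 restricts efficacy analyses to scheduled measurements. Collecting a scan does not oblige the sponsor to use it, and a subject without a scheduled scan is simply missing the outcome. The week lists are indeed consistent, so it would be wrong to call the omission a slip. SAP 2.5.3 does not settle the matter, however. The rule sits under unscheduled visits, its stated reason is fluctuation around a relapse, and Early Withdrawal is a protocol-defined visit that it does not name. Even if the omission is intended, set and denominator still disagree.

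A second reply is that the set in SAP 2.2.3 could be read as requiring a scan that counts for the endpoint. That would remove the Gd problem for a subject scanned only at withdrawal. But the set is defined once for all MRI analyses, and a Week 12 scan satisfies it without supplying any T2 read.

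Third, sensitivity analysis 5 in SAP 2.4.2 applies multiple imputation for dropouts to these same endpoints. It does address informative dropout in part, but it neither uses the observed withdrawal scan nor defines the offset in the confirmatory model.

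A reader might infer that every dropout loses a last scan, about 22 per arm at 10%. The documents do not support that. The withdrawal MRI may be skipped if a recent one exists; Protocol 3.3 stops data collection when consent is withdrawn unless a further consent form is signed; and SAP 2.4.3.2 excludes scans within 30 days of systemic corticosteroids.

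**Conclusion.** The point holds on the text as written. Two gatekeeping endpoints omit a count that the plan has centrally read, and their denominator can be zero for members of their own analysis set. None of the other denominator descriptions cures this, since each can count scans or time without the matching lesions.

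The size is modest and uncertain: about 1 to 11 per arm for Gd and 3 to 22 for T2, under assumed dropout of 5% to 20% of 220 with even or early timing. These are upper bounds on the early withdrawers the change would recover, because not all of them will have a usable withdrawal scan.

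A reader might go on to infer that the Gd or T2 comparison is biased, or that the test result would change. Neither is shown: the documents give no dropout pattern by arm and no lesion activity among withdrawers. Nor does the point extend to the brain and lesion volume models, which are built on scheduled nominal visits. It warrants a change to the SAP before database lock and does not put the design in question.

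**What to change.** In SAP 2.4.3.2, for both Gd and T2:

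- add the valid Early Withdrawal count to the numerator, and add that scan to the scan count in the offset;
- define the offset as the log of the number of scans that contribute a read to that endpoint, so that the Week 12 scan counts for Gd and not for T2;
- require at least one contributing scan for inclusion in that endpoint's analysis, and report how many subjects fail this by arm.

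Then align the denominator wording in Protocol 8.9.2, the derivation table and the model text. Leave the brain and lesion volume models as they are, and keep the T2 offset a scan count.

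The cost is SAP wording and programming; no new data are needed. The downside is that some withdrawal scans are off treatment. The 4-week window runs from withdrawal from the study, so the gap since the last dose may be longer. The version restricted to scheduled scans can be kept as a sensitivity analysis, with the same requirement of at least one contributing scan.
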